This will be a prospective double-blinded randomized placebo control trial of women ≥20 weeks of gestation with persistent antepartum hypertension (sustained SBP ≥160 or DBP ≥110 mmHg) and a wide pulse pressure (>60 mmHg) who meet all inclusion criteria and have no exclusion criteria. It is routine that laboratory studies are performed on admission for all women with hypertensive disorders. If electrolyte disturbances exist, therapy will not be initiated unless the electrolyte is normalized or repleted.

After informed consent and upon meeting inclusion criteria with severe range hypertension with wide pulse pressure, the study personnel will inform pharmacy personnel who will then randomly assigned the patient to groups by opening the next previously prepared sequential and numbered opaque study envelope. Participants will be randomized to furosemide plus an antihypertensive versus placebo containing normal saline and an antihypertensive. The pharmacy staff will send the assigned treatment. which will be administered by the bedside nurse. The vials containing the treatment will be indistinguishable as both furosemide and normal saline placebo are clear, colorless solutions. Thus, the provider, nurse, and patient will be blinded to the treatment. The choice of antihypertensive will be determined by the primary OB provider. At our institution, this will be one or more of the recommended medications for urgent blood pressure control as outlined by the American College of Obstetricians and Gynecologists Practice Bulletin on gestational hypertension and preeclampsia. These include IV labetalol, IV hydralazine, or immediate-release oral nifedipine. As meta-analyses have not shown that one of the aforementioned antihypertensives is superior than another, and all are reasonable options, the choice of antihypertensive will be left up to the OB

Version 2

Protocol Number I

provider^{8,9}. This will also improve the generalizability of the study as it does not interfere with what is typically done in clinical practice.

As a procedure of the study, patients will have their blood pressure recorded at least every 15 minutes up to one hour after administration of the study drug. Thereafter, as part of routine care, patients in both groups will receive similar antepartum surveillance, including blood pressure and pulse assessment every four hours or more frequently if vital signs are abnormal, daily weight measurement, and daily urinary output measurements.

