Study Procedures

- 1. Antepartum patient diagnosed with a hypertensive disorder in pregnancy.
- 2. Patient approached for study participation and informed consent obtained if interested.
- 3. Patient develops severe range BP (SBP>160 and/or DBP>110) with increased pulse pressure (>60mmHg). This will be considered baseline BP.
- 4. When ordering provider's choice of antihypertensive, pharmacy notified that patient is study participant and randomizes patient by choosing from sequential opaque envelope.
- 5. a. Patient randomized to treatment arm and receives 40mg /4mL IV furosemide in addition to usual antihypertensive.
 - b. Patient randomized to placebo and receives 4mL normal saline in addition to usual antihypertensive.
- 6. Blood pressure check every 15 minutes after administration of furosemide/placebo for four recordings (15, 30, 45, 60 minutes)

2. Data analysis

Specify statistical and analytical methods (statistical power, sample size, significance level, etc.).

The primary outcome variable is reduction in mean systolic BP during the 1-hour period after drug administration. BP will be taken every 15 minutes for 1 hour and averaged. Intention-to-treat analysis will be performed. This study will use a two-sided t-test with the null hypothesis set at the standard significance level (p –value < 0.05), to determine if the addition of furosemide to usual antihypertensive significantly reduces blood pressure.

Change in average BP from baseline will be tested comparing the group receiving furosemide and the group receiving placebo using Mann-Whitney U, as BP usually presents as a non-parametric continuous variable. Multivariate regression will be used to adjust for potential confounders, such as maternal age, BMI, diabetes, baseline BP, antihypertensive chosen by the primary obstetrician, number of doses of antihypertensive, and gestational age. Comparative testing will be done to explore differences between the furosemide and placebo groups. Continuous variables satisfying the assumption of normality will be tested using the Student t-test and means and standard deviations will be reported. Otherwise, variables will be tested using the Mann-Whitney U test and will be reported using medians and interguartile ranges. The x2 or

Version 2

Protocol Number I

Fisher exact test will be utilized to test categorical variables and sample sizes and percentages will be reported.

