A power calculation was completed using OpenEpi, Version 3, open source calculator—SSMean. The assumption of normality and that both groups will have the same common variance was applied. We set the standard deviation value as 20mmHg in the power calculation, which is based on pilot data from our own practice as well as data found in a randomized clinical trial using furosemide versus placebo (Ascarelli et al, Ob/Gyn 2005). A 15mmHg reduction in mean systolic blood pressure in the placebo group compared with the IV furosemide group was considered to be clinically significant as this represents an attainable, yet safe reduction from severe to mild range blood pressure. Using the 2-group Student t-test of equal means, 28 patients per study arm for a total of 56 patients would be required to detect a difference of 15mmHg with 80% power and a significance level of p=0.05. Once data has been collected, we will test for normality and use the appropriate statistical tests.

To account for patients who withdraw from the study or who need to be excluded after consent, 35 per arm or 70 total patients are to be enrolled. A randomization schedule will be created using block randomization with 10 blocks of 10 participants allocating randomization numbers to drug or placebo. The numbers will be sequentially assigned to participants by the pharmacist on duty. The hospital pharmacy will maintain the master list of the randomization log with patient study identifiers.

Data monitoring

Describe data monitoring methods for studies with more than minimal risk (i.e. data monitoring committee). Explain adverse event reporting procedures.

This is a greater than minimal risk study. Adverse events will be reported to the sub-investigator and primary investigator by the nurse and/or the obstetric provider. Furthermore, the sub-investigator will be actively following study participants closely to monitor for adverse events. If found, these will be reported to the institutional review board according to their reporting polices.

3. Data storage, security, and confidentiality

Describe where data will be stored and how data will be secured during the study. Provide information on confidentiality measures (coding, storage mechanisms, etc.). Indicate who will have access to the data and how the data will be used. If subject identifiers will be released, describe to whom and for what purpose the data will be released.

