Endocrine & metabolic: Glycosuria, hyperglycemia, hyperuricemia, increased serum cholesterol, increased serum triglycerides

Gastrointestinal: Abdominal cramps, anorexia, constipation, diarrhea, gastric irritation, mouth irritation, nausea, pancreatitis, vomiting

Genitourinary: Bladder spasm

Hematologic & oncologic: Agranulocytosis, anemia, aplastic anemia, eosinophilia, hemolytic anemia, leukopenia, purpura, thrombocytopenia

Hepatic: Hepatic encephalopathy, intrahepatic cholestatic jaundice, liver enzymes increased

Hypersensitivity: Anaphylaxis, anaphylactoid reaction, anaphylactic shock

Immunologic: DRESS syndrome

Neuromuscular & skeletal: Muscle spasm, weakness

Ophthalmic: Blurred vision, xanthopsia

Otic: Deafness, tinnitus

Renal: Interstitial nephritis (allergic), renal disease

Miscellaneous: Fever

Source: https://www.uptodate.com/contents/furosemide-drug information?search=furosemide&source=panel_search_result&selectedTitle=1~148&usa ge type=panel&kp tab=drug general&display rank=1

Version 2

Protocol Number I

3. Protection against risk(s)

Describe how the study will minimize or prevent any potential risks. Techniques to minimize risk include subject monitoring, withdrawal criteria, and follow-up procedures.

Subjects will be monitored for side effects and dosage levels will be adjusted if the subject experiences side effects from furosemide. Subjects will not receive additional furosemide if side effects are deemed significant. Subjects will be allowed to withdraw from the study at any time without consequence. If new information about the study becomes available, subjects will be informed and re-consented if applicable.

4. Potential benefit(s) to the subject

Describe any potential medical benefit(s) for subject participation. State if participation results in no benefit to the subject.

The direct medical benefits to the subject for participating in the study include acute control of severe hypertension, which reduces the risk of stroke, placental abruption, hypertensive encephalopathy, and myocardial infarction. An additional benefit may include prolongation of pregnancy at critical gestational ages which may reduce the risks of prematurity which includes respiratory distress, intraventricular hemorrhage, necrotizing enterocolitis, and metabolic and thermic dysregulation.

5. Alternative to participation

Describe any alternative therapies or courses of action available to the subject if they decide not to participate in the study.

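### Does the risk section's promise to adjust furosemide dosage, in a trial whose procedures list one fixed blinded administration, require a change to the plan?

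*Combined protocol and SAP*

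**What the plan says.** Section IV.3 (Protection against risk(s)) contains two sentences that bear on drug exposure. The first is: "Subjects will be monitored for side effects and dosage levels will be adjusted if the subject experiences side effects from furosemide". The second is: "Subjects will not receive additional furosemide if side effects are deemed significant". It also allows withdrawal at any time and promises to pass on new information, with renewed consent where applicable.

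Section III.1 (Methods and procedures) sets out what is done.

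- Step 5a: "Patient randomized to treatment arm and receives 40mg /4mL IV furosemide in addition to usual antihypertensive".
- Step 5b: "Patient randomized to placebo and receives 4mL normal saline in addition to usual antihypertensive".
- Step 6, the last numbered step, takes four blood pressure readings at 15, 30, 45 and 60 minutes. The narrative then hands patients over to routine surveillance.

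On masking, the same section says: "Thus, the provider, nurse, and patient will be blinded to the treatment". Pharmacy opens the envelope and sends the treatment. Under Section III.2 (Data analysis) pharmacy also keeps the randomization log.

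Section III.2 defines the primary outcome as "reduction in mean systolic BP during the 1-hour period after drug administration", analysed by intention to treat. The data monitoring paragraph states: "This is a greater than minimal risk study".

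**The concern.** Read together, the sections seem to describe two different trials. Adjusting a dosage level needs a later dose or a second level, and Section III has neither. Refusing additional furosemide implies that more might have been given.

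Both sentences also name furosemide rather than blinded study drug, although the bedside staff who would act on them do not know the arm, and no unblinding procedure is described.

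Two things would be at stake. First, in a study classed as above minimal risk, protections on paper that cannot be used would overstate how risk is controlled. Second, if staff did act on the risk section by changing or repeating study drug, the blind and the one-hour window of the primary outcome could be disturbed for that patient.

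**Working it through.** The question is textual, so the sections are set side by side.

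**1. What Section III schedules.** Step 3 fixes the baseline reading. Step 5 gives one amount per arm. Step 6 gives four readings timed from that administration. Routine care follows, with no further study drug mentioned. The regression in Section III.2 adjusts for how many antihypertensive doses were given but has no term for the number of study-drug doses. All of this fits one administration. The word single is not used, so this is an inference, though a well-supported one.

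**2. Each measure in Section IV.3 against Section III.**

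| Measure | Counterpart in Section III | Status |
|---|---|---|
| Monitoring for side effects | Close follow-up by the sub-investigator; reports from nurse and obstetric provider | Workable |
| Adjusting dosage | None | No matching procedure |
| Withholding additional furosemide | No later study dose listed | Met automatically if given once |
| Withdrawal at any time | Return to regular care, described under transition from participation | Workable |
| New information and renewed consent | None needed | Workable |

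The count is 1 without a procedure + 1 redundant + 3 workable = 5. A redundant rule does not contradict the procedures, so the firm conflict is one clause.

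**3. Effect on the estimate.** The primary outcome uses the step 3 baseline and the mean of the four step 6 readings. With step 5 followed, no dose is adjusted, so every value entering that mean is the same with or without the clause.

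**4. Effect on the sample size.** The inputs in Section III.2 are a difference of 15 mmHg, a standard deviation of 20 mmHg, 80% power and a two-sided 0.05 level. By the normal approximation, n = 2 × (1.96 + 0.8416)² × 20² / 15² = 2 × 7.849 × 400 / 225 = 27.9, which rounds up to the stated 28 per arm. No input depends on a dose-adjustment rule.

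**5. If someone tried to act on the clause.** Bedside staff would have to go through pharmacy, which prepares the treatment and holds the list. Pharmacy could supply a matched change without disclosing the arm, so loss of the blind does not follow automatically, although the protocol describes no such route. The narrative in Section III.1 ties quarter-hourly readings to administration of study drug, so the same rule could reasonably apply again after a further administration. Step 6 follows step 5, which still anchors the primary window to the listed administration.

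**6. Other protections.** The exclusions cover low potassium on admission, anuria or renal failure, previous diuretic or potassium use, and known reaction to furosemide. Electrolyte disturbances must be corrected before therapy. After the first hour there are regular vital signs, daily weight and daily urine output. None of these relies on the disputed clause.

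**The case for a change.** The strongest case for a change is that a protocol for a study above minimal risk should not promise a protection it cannot deliver, and that the section on minimizing risk is where such a promise matters most. Staff masked to treatment cannot tell whether a side effect comes from furosemide, and nothing tells them what to do next. Section III never says that study drug is given only once, so the reader is left to infer it. If further doses were intended, Section III omits them, and their timing relative to the four readings would need stating. On either reading some text is wrong, and correcting it costs only words.

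Part of this stands. The adjustment clause has no matching procedure, no unblinding route is described, and on its face Section IV.3 disagrees with steps 5 and 6.

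The rest is weaker. The sentence on additional furosemide is harmless if study drug is given once. It might instead concern furosemide given by the treating clinician; Section IV.5 mentions such use for women who decline the study, but no section says this is what was meant. Naming the drug in a section about that drug's risks is a matter of style. Harm to the blind or the outcome window requires a repeat or altered dose that no procedure provides for. Any figure put on that harm would describe an invented scenario.

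**Conclusion.** The concern correctly identifies a wording mismatch, and Section IV.3 and steps 5 and 6 of Section III must be reconciled as an editorial matter. It does not call for a change to the design, conduct or analysis. Its size is one clause of five in Section IV.3 without a counterpart. With Section III followed, the effect is nil on patient exposure, on the primary outcome and on the 28 per arm. Rewording would change neither what the trial does nor what it can conclude.

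This rests on two assumptions: that study drug is given as steps 5 and 6 list it, and that staff work from those steps rather than from the risk narrative. If repeat or adjusted dosing was in fact intended, Section III would be incomplete and the conclusion would have to be revisited. No view is taken here on which dosing rule is right.
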